7.6.2.3 CBT-I Treatment Assessment Visit Three

- This will occur in person about seven weeks from the date of randomization (during the COVID pandemic, this will be modified to occur over the telephone to the extent possible);
- The following procedures will be completed at this visit:
 - The patients will return the actiwatches;
 - The online or paper sleep diaries will be reviewed and/or collected;
 - The dialysis days and the start time for the scheduled shift for the preceding seven day will be recorded; and
 - The case-report form on cumulative weekly use of sedatives/hypnotics and opiates will be completed, assessing the use of sleep aids for the preceding 7 nights.
- The patients will be scheduled to receive a phone call for the 7-week CATI.

7.6.3 Medication Visits

For patients randomized to trazodone and medication placebo, the visits and related procedures will be identical.

7.6.3.1 Medication Assessment Visit One

- This visit will occur in-person and, to the extent possible, on the day of the first dialysis treatment of the first week following randomization (during the COVID pandemic, this will be modified to occur over the telephone to the extent possible); and
- The patients will be provided with three-week supply of 50-mg trazodone or matching placebo. The patients will be provided with a sufficient supply of drug to increase the dose of the medication to 100 mg starting week 2.

7.6.3.2 Medication Assessment Visit Two

- The visit will occur over the telephone and, to the extent possible, on the day of the first dialysis treatment of the second week following randomization and one week following the “Medication Assessment Visit One”;
- The coordinator will ask the patient if they have been prescribed any new medications since the last visit to screen for contra-indicated drugs to prolong QTc;
- The patients’ response to drug therapy will be assessed and they be advised to:
 - Continue on the 50 mg dose if they are satisfied with their sleep over the previous 7 days; or
 - Increase to 100 mg for patients with persistent problems with sleep in the previous 7 days.

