4.1 Study Population

4.1.1 Inclusion and Exclusion Criteria:

Inclusion Criteria:

1. Age \geq 18 years;
2. Undergoing thrice-weekly maintenance HD for \geq 3 months;
3. Able to speak English;
4. ISI score \geq 10 at pre-screening with sleep disturbances for \geq 3 nights per week for \geq 3 months.

Exclusion Criteria:

1. Severe depression assessed by Patient Health Questionnaire-2, PHQ-2 and if appropriate, Patient Health Questionnaire-9 [120];
2. Suicidal Ideation;
3. Alcohol abuse on CAGE questionnaire (score \geq 2) or substance abuse on DAST-10 questionnaire (score $>$ 5) [121, 122];
4. Severe restless leg syndrome;
5. Treatment with trazodone in the past one month;
6. Known allergy to trazodone (self-report or by chart review);
7. Current treatment with monoamine oxidase inhibitors or in the preceding 14 days (Appendix Four);
8. Current treatment with linezolid (self-report or by chart review);
9. Current treatment with other drugs that are inhibitors of CYP3A4 (e.g., itraconazole, clarithromycin, voriconazole), or known to prolong QT interval including Class 1A antiarrhythmics (e.g., quinidine, procainamide) or Class 3 antiarrhythmics (e.g., amiodarone, sotalol), antipsychotic medications (ziprasidone, chlorpromazine, thioridazine), and quinolone antibiotics (Appendix Four);
10. Pregnancy, or lactation, or women of childbearing potential not willing to use adequate birth control;
11. Life Expectancy $<$ 3 months;
12. Expected to receive a kidney transplant or transition to home dialysis (peritoneal dialysis or home HD) within 6 months;
13. Any other condition including cognitive impairment that, in the opinion of the investigator, should preclude patient participation in the clinical trial.

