7.2 Screening

- This will occur in-person, within 10 days of completion of pre-screening;
- Patients with ISI score ≥ 10 will be invited to sign an informed consent form to complete screening activities;
- The demographic information of all patients who consent to participate in the study will be recorded and they will be registered on the online portal;
- The following assessments will be completed (during the COVID pandemic, these may be administered over the telephone):
 - Medication Review to ascertain current use of trazodone or in the preceding one month;
 - Patient Health Questionnaire-2 (PHQ-2); if score on PHQ-2 is ≥ 3 , PHQ-9 will be administered (score for exclusion, ≥ 20). Patients who answer “more than half the days” or “nearly every day” to question 9 of the PHQ-9 will be administered the Columbia Suicide Severity Rating Scale to determine the suicidal intent; those with suicidal ideation will be excluded;
 - CAGE questionnaire for alcohol abuse (score for exclusion ≥ 2) and DAST-10 for substance abuse (score > 5);
 - Cambridge-Hopkins Restless Legs syndrome questionnaire (criteria for exclusion – answer to question 11, moderately or extremely distressing, AND, answer to question 12, 4-5 days per week or every day);
 - Medical history for co-existing illnesses;
 - For women that have had menstrual periods in the last 12 months, will be asked if they are pregnant or currently lactating. Pregnancy will be further excluded by a blood pregnancy test for women randomized to trazodone or medication placebo; and
 - Final review of inclusion and exclusion criteria;
- Eligible participants will be provided with instructions to complete sleep diaries for the run-in period:
 - Patients that choose to complete the sleep diaries online will be provided with log-in details and instructions on how to enter the data in the web-portal;
 - Patients who choose to use the paper-form of sleep diaries will be provided with the sleep diary for the first week along with instructions on how to enter the data;

- The patients' nephrologist will be informed about their enrollment in the clinical trial and if randomized to drug therapy, with a list of medications that could prolong QTc in patients treated with trazodone, as listed in the FDA package insert for the drug;

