7.4 Baseline Visit

- This will occur in-person seven days after the start of the run-in period and to the extent possible, on the first dialysis day of the week (Monday or Tuesday) (during the COVID pandemic, this will be modified to occur over the telephone to the extent possible); and
- The following procedures will be completed at this visit:
 - The patients will return the actiwatches;
 - The online or paper sleep diaries will be reviewed and/or collected;
 - The dialysis days and the start time for the scheduled shift for the preceding seven days; and
 - The case-report form on cumulative weekly use of sedatives/hypnotics and opiates will be completed, assessing the use of sleep aids for the preceding 7 nights.
- The patients will be scheduled to receive a phone call for the baseline CATI.

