7.5 Randomization

- This will occur electronically through the web-based portal after CATI is completed, and to the extent possible, the same week as the “Baseline” visit and the baseline CATI, and no more than 25 days after pre-screen with ISI;
- Patients will be randomly assigned to telehealth CBT-I, trazodone, or medication placebo, stratified by site using blocks of varying size to ensure that the three groups are balanced at periodic intervals; and
- The patients should begin treatment within 10 days from the date of randomization (first CBT-I session or provided with the first supply of medication).

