Appendix Three: Study Schedule

	Pre-Screen	Screen	Run-In		Treatment						Follow-up from Randomization		
WEEK			-1	0	1	2	3	4	5	6	7	13	25
Insomnia Severity Index	x			x				x			x	x	x
Structured Interview, Inclusion/Exclusion Criteria		x											
Randomization				x									
CBT-I Telehealth Visits*					x	x	x	x	x	x			
CBT-I Visits (coordinator)							x			x			
Trazodone/Placebo In-Person Visits					x			x		x			
Trazodone/Placebo Telephone Visits						x	x						
Treatment Adherence Assessment							x		x		x	x	
CATI				x			x				x	x	x
Actigraphy with sleep diary			x						x				x
Concomitant Sedatives/Hypnotics				x			x				x	x	x

*Patient randomized to CBT-I will maintain sleep diaries for each of the six-week treatment period

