Appendix Eight: COVID Risk Mitigation Plan for SLEEP-HD

Pre-screening (ISI)	In person (need <5 minutes which are very important to build up the rapport with the patient)
Consent & Screening	In person - Consent process Screening questionnaire packet (as much as possible in person) On phone/online Any screening questions not completed in person Review of EMR for inclusion/exclusion determination
Run-In visits	In person 
 1) Actiwatch placement & instruction, sleep diary delivery & instruction, CBT Manual delivery On phone/online 
 2) randomization, CATI, sedative/hypnotics 
*Participants can return Actiwatches and completed diaries to unit where RC's will pick up, OR mail back to RC's. Watches and diaries will be placed in sealed ziplock bag and kept untouched for 3-4 days.

Treatment visits	In person 
 3) Actiwatch placement & instruction, sleep diary delivery & instruction Mail 
 4) Drug delivery/collection (can be done the inter-office mail or US Postal Service with return label directly to the patient; follow-up with a phone call) On Phone/online 
 5) Study Medication Follow-Up Visits (all via phone). 6) Visit Assessments and sedative/hypnotics can be done via phone/online. 7) CATI calls over the phone/online. 
*Participants can return Actiwatches and completed diaries to unit where RC's will pick up, OR mail back to RC's. Watches and diaries will be placed in sealed ziplock bag and be kept untouched for 3-4 days.

Drug collection	Collection process

	
 1) Patient brings bottle to dialysis unit, to hold at unit for coordinator or to be sent to research team through inter-office mail 2) Keep it untouched in zip lock bags for 3-4 days 3) Use mask and gloves during accountability and sanitize the bag 4) Drop off at pharmacy in zip lock bag (UNM) or store in research office (UW).

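### Barred concomitant drugs (exclusions 7 to 9) are reviewed at Screening and not re-checked before the first study drug supply at least 7 days later; on-treatment questions name only QTc drugs

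*Combined protocol and SAP*

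**What the plan says.** Section 4.1.1 sets three drug exclusions. Exclusion 7 has a look-back: "Current treatment with monoamine oxidase inhibitors or in the preceding 14 days". Exclusion 8 bars current linezolid. Exclusion 9 bars CYP3A4 inhibitors or, as an alternative ground, drugs known to prolong the QT interval. Appendix Four lists the products.

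Eligibility is settled at Screening (7.2), whose list includes "Final review of inclusion and exclusion criteria". Appendix Three has a single mark in the row "Structured Interview, Inclusion/Exclusion Criteria". The COVID plan (Appendix Eight) puts "Review of EMR for inclusion/exclusion determination" under consent and screening, and lists nothing comparable under the run-in.

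The 7-day run-in starts once screening is complete. At its end, the Baseline Visit (7.4) has one medication item: "The case-report form on cumulative weekly use of sedatives/hypnotics and opiates will be completed". Section 7.5 then allows a further delay: "The patients should begin treatment within 10 days from the date of randomization". At Medication Visit One (7.6.3.1), "The patients will be provided with three-week supply of 50-mg trazodone or matching placebo"; no medication question is listed there.

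At Visits Two to Five (7.6.3.2 to 7.6.3.5) the coordinator asks, in the same words each time, about "any new medications since the last visit to screen for contra-indicated drugs to prolong QTc". Section 7.2 also has the nephrologist of a patient randomized to drug therapy receive a list of QTc-prolonging drugs.

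**The concern.** The exclusions protect patients who may receive trazodone, so the date that matters is the first dose. The check is tied to Screening instead. A patient who starts a listed drug during run-in could reach the first dose without being asked, and the Visit Two question looks back only to Visit One. That holds even for a QT-prolonging drug, the group the plan watches most closely.

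The event is plausible. Section 9.2 names infections among the adverse events anticipated in this population, and 14 of the Appendix Four rows are anti-microbials. The plan also treats new prescriptions as worth asking about at four visits, but not at the visit that precedes exposure. For a different exclusion, pregnancy, it does specify a test tied to allocation to a drug arm (7.2). Exclusions 7 to 9 have no equivalent.

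A second, smaller gap is that the on-treatment question states a narrower purpose than the exclusions. A coordinator told to look for QTc drugs has no written instruction to act on a new MAO inhibitor, linezolid, or a CYP3A4 inhibitor that does not prolong QTc.

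**Working it through.** The plan states no figure to reproduce. The check is a trace of the listed steps, followed by addition of the visit windows.

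**Trace**

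| Step | Medication item listed | Exclusions 7 to 9 covered? |
|---|---|---|
| Screening (7.2) | Trazodone use; final criteria review | Yes |
| Baseline CATI (7.3) | None | No |
| Baseline Visit (7.4) | Sleep aids and opiates, previous 7 nights | No |
| Randomization (7.5) | None | No |
| Medication Visit One (7.6.3.1) | None; first supply given | No |
| Visits Two to Five (7.6.3.2 to 7.6.3.5) | New prescriptions since last visit | QTc drugs named; others not |

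Under Appendix Eight the run-in lists only randomization, CATI and sedatives/hypnotics as phone or online items, and drug may be mailed.

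**Length of the unchecked interval**

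Inputs: run-in 7 days (7.2); Screening 0 to 10 days after pre-screening (7.2); randomization no later than day 25 after pre-screening (7.5); first supply within 10 days of randomization (7.5). Let *s* be the day of Screening.

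- Shortest: the run-in alone, 7 days.
- Longest within the stated windows: 25 + 10 − *s*. With *s* = 0 this is 35 days; with *s* = 10 it is 25 days.
- Intended path: a 7-day run-in, randomization in the same week as the Baseline Visit, and Visit One in the first week after randomization, so about 7 to 14 days.

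**Exclusion 7**

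Of the 14 days before first dose that this exclusion treats as relevant, the unchecked part is min(gap, 14). A gap of 7 days leaves 7 unchecked; a gap of 14 or more leaves all 14. A patient who was clear at Screening is at risk only if an MAO inhibitor is newly started in that time.

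**On-treatment target**

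Appendix Four has 14 anti-microbial rows + 39 other rows = 53 rows, with 26 distinct generic names. It does not label drug classes, so the MAO inhibitor grouping below is by ordinary pharmacological class.

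- MAO inhibitors (rasagiline, selegiline, isocarboxazid, phenelzine, tranylcypromine): 7 rows, 5 generics.
- Linezolid: 1 row, 1 generic.
- Together: 7 + 1 = 8 rows and 5 + 1 = 6 generics, barred under criteria separate from QT.
- CYP3A4 inhibitors named in exclusion 9: clarithromycin 2 + itraconazole 2 + voriconazole 1 = 5 rows, 3 generics. Some of these may also count as QTc drugs.

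All four on-treatment questions name QTc as the target.

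**The case against.** The strongest case is that little is really missing.

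- The question at Visits Two to Five covers any new prescription, so it would bring out linezolid as readily as a QTc drug, and section 4.3 lets the investigator stop treatment for significant risk. This stands: the on-treatment part is mainly wording. It does not touch the gap before first dose.
- Exclusions 7 to 9 are eligibility criteria, and the plan never makes them on-treatment prohibitions. This is a fair reason to rank the on-treatment part second.
- Other contacts fall inside the interval. The nephrologist's QTc list depends on allocation, so it goes out around first supply; a record review supplements the baseline sleep-aid assessment (6.2); a site investigator prescribes (5.3.1) and a pharmacy dispenses (5.3.2). Any of these might catch a barred drug, but none is written as a check of exclusions 7 to 9. The nephrologist's list is a notice, and the record review serves an outcome.
- The Visit Two look-back could be taken to run from the last medication review. The text allows that reading but does not state it.
- The Manual of Operations (10.3) may contain the check. It is not among the documents, so the finding concerns the protocol as written, not site practice.
- The 35-day figure is not a strict maximum, because 4.2.1.1 allows a repeat ISI when a window expires, and brand-row counts do not measure exposure. Both points stand.

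**Conclusion.** The concern holds. As written, exclusions 7 to 9 are reviewed at Screening and no listed step re-checks them before first supply, at least 7 days later and about 7 to 14 days on the intended path. Read literally, the first on-treatment question does not reach back into that interval. The narrower QTc target at Visits Two to Five is a secondary wording gap.

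This rests on two things: that the listed visit steps are complete, and the literal reading of the look-back at Visit Two. No patient count is offered, because the documents give no rate of new listed prescriptions. It should be fixed because a patient could receive trazodone on a barred drug without being asked, and closing the gap costs little. It has no bearing on the estimand, power or alpha.

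**What to change.** 1. At Medication Visit One, in both drug arms and before drug is handed over or mailed, ask about medications started since Screening and compare the answers with Appendix Four.
2. At Visits Two to Five, restate the purpose of the question as finding any drug that is in Appendix Four or otherwise meets exclusions 7 to 9.
3. Send the nephrologist the Appendix Four list together with the QTc list.

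The cost is protocol wording and one question at an existing contact, using a list that already exists. The downside is that a few randomized patients may have their first supply delayed or withheld. They should still be followed for outcomes, as section 4.3 provides when treatment is stopped, and stay in the intention-to-treat analysis.

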7.6.3.3 Medication Assessment Visit Three

- The visit will occur over the telephone and, to the extent possible, on the day of the first dialysis treatment of the third week following randomization and one week following the “Medication Assessment Visit Two”;
- The coordinator will ask the patient if they have been prescribed any new medications since the last visit to screen for contra-indicated drugs to prolong QTc;
- The patients’ response to drug therapy will be assessed and they be advised to:
 - Patients who have been on 50 mg dose will be assessed and based upon patients’ satisfaction with their sleep will either continue with the 50 mg dose or the dose will be increased to 100 mg;
 - Patients who had been on 100 mg dose will be assessed and based upon patients’ tolerability of the higher dose will either continue with the 100 mg dose or the dose will be decreased to 50 mg.

7.6.3.4 Medication Assessment Visit Four

- The visit will occur in-person and, to the extent possible, on the day of the first dialysis treatment of the fourth week following randomization and one week following the “Medication Assessment Visit Three” (during the COVID pandemic, this will be modified to occur over the telephone to the extent possible);
- The coordinator will ask the patient if they have been prescribed any new medications since the last visit to screen for contra-indicated drugs to prolong QTc;
- The medication bottle provided to the patient on the prior visit will be collected;
- The coordinators will perform a pill count to assess adherence for the preceding 7 days;
- The dialysis days and the start time for the scheduled shift for the preceding seven days will be recorded;
- The patients will be provided with a three-week supply of trazodone or medication placebo at the same dose that they were on the prior week;
- The case-report form on cumulative weekly use of sedatives/hypnotics and opiates will be completed, assessing the use of sleep aids for the preceding 7 nights; and
- The patients will be scheduled to receive a phone call for the 4-week CATI.

7.6.3.5 Medication Assessment Visit Five

- The visit will occur in-person and, to the extent possible, on the day of the first dialysis treatment of the sixth week following randomization and two weeks following the “Medication Assessment Visit Four”;
- The coordinator will ask the patient if they have been prescribed any new medications since the last visit to screen for contra-indicated drugs to prolong QTc;
- The patients will be reminded to start maintaining online or paper sleep diaries; and
- The coordinator will place the actiwatch on the patient and provide instructions on wearing the device. The actiwatch will be placed on the arm opposite to the upper extremity with the functional arteriovenous access being used for dialysis. In patients with a lower extremity arteriovenous access or with a central venous catheter, the actiwatch will be placed on the non-dominant arm.

7.6.3.6 Medication Assessment Visit Six

- The visit will occur in-person and, to the extent possible, on the day of the first dialysis treatment of the seventh week following randomization and one week following the “Medication Assessment Visit Five” (during the COVID pandemic, this will be modified to occur over the telephone to the extent possible);
- The medication bottle provided to the patient on the prior visit will be collected;

- The coordinators will perform a pill count to assess adherence for the preceding 14 days;
- The online or paper sleep diaries will be reviewed and/or collected;
- The dialysis days and the start time for the scheduled shift for the preceding seven days will be recorded;
- The patients will return the actiwatches;
- The case-report form on cumulative weekly use of sedatives/hypnotics and opiates will be completed, assessing the use of sleep aids for the preceding 7 nights;
- The patients will be scheduled to receive a phone-call for the 7-week CATI; and.
- If the patient wants to continue trazodone past the six-week treatment period, the site investigator will facilitate the treatment plan in partnership with the primary nephrologist and/or the primary care physician.

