5.3.2 Drug Procurement and Dispensation

Prior to launching the clinical trial, the Investigational Drug Services at Harborview Medical Center, where the PI is based, will procure 50-mg tablets of trazodone from the same manufacturing stock for both clinical sites and prepare matching placebo. A supply of the study medications will be shipped to the Investigational Drug Services at Albuquerque in New Mexico. The medications will be dispensed as per the protocol by the Investigational Drug Services at each site and the study coordinators will hand the study drug to the participants at the dialysis facility when they arrive for their routine HD treatments (during the COVID pandemic, this will be modified to allow coordinators to leave drug with dialysis unit or mail drug via US postal service or inter-office mail); this will occur once during week 1 where a 3-week supply of the drug will be provided (with

capacity to increase the dose to 100 mg starting week 2), and at week 4 where a -week supply of the drug for the dose being taken during week 3.

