6.1 Patient-Reported Outcomes

The primary (ISI) and secondary patient reported outcomes will be ascertained by Computer-Assisted Telephone Interviewing (CATI) at weeks 0, 4, 7, 13, and 25 from randomization by interviewers blinded to the study assignment. The baseline assessment will be performed during the run-in period and prior to randomization. The CATI will run out of Albuquerque, NM under the direction of [name] who will train the interviewers. CATI operators will conduct the assessments using scripts prepared for the call. The interview is expected to last about 30 minutes.

The order of preference for the day of the week for completing CATI, from optimal to the least preferred, is as follows:

- The day following the first dialysis treatment of the week (Tuesday for patients on a Monday-Wednesday-Friday schedule, and Wednesday for patients on a Tuesday-Thursday- Saturday / Sunday-Tuesday-Thursday schedule);
- The day following the second dialysis treatment of the week – Thursday, or Friday, respectively, for patients on a Monday-Wednesday-Friday or Tuesday-Thursday- Saturday/Sunday schedule;
- Within the first hour of the dialysis session according to the patient's treatment schedule as noted above.

To the extent possible, the calls for the 4, 7, 13, and 25 weeks will be done on the days as for the baseline call for the patient. If there are individuals that do not have access to a telephone, the study staff will make that available to them to complete the CATI.

If all attempts to complete a follow up CATI call are unsuccessful, the Principal Investigator may authorize the site study coordinator to complete the PROs using paper forms at the bedside. We anticipate this approach to be used only under exceptional circumstances, if at all.

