7.6.4.2 Seven Week CATI

- This will occur over the telephone at seven weeks from the date of randomization;
- A research assistant from Albuquerque, NM will call the patient to initiate the CATI;
- The following assessments will be completed:
 - Insomnia Severity Index (primary outcome measure); and
 - Seven pre-specified secondary patient-reported outcome measures; and
- A system-configured email will be sent to the site study coordinator upon successful completion of CATI.

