4.1 Performance Monitoring

Performance monitoring will be an ongoing activity performed by the study Principal Investigator and statistician, and status reports will be reviewed by the DSMB during their regular meetings. Procedural reviews to address protocol adherence with respect to patient recruitment and eligibility, retention and follow-up, randomization and blinding, and quality of data will be conducted and monthly reports generated.

Performance data will be reviewed in aggregate and by site. It is expected that:

- (1) the overall enrollment rate will not drop below the expected rate by more than 50%; and
- (2) the response rate for the ISI by CATI will be no less than 85% at the 7-week time-point among those randomized to CBT-I, trazodone, or placebo;

Data will be entered on-line into a REDCap database hosted at the Data Coordinating Center (DCC). Data will be entered into fields with automated validation and logical checks built in. Outcome measures will be collected by Computer Assisted Telephone Interview (CATI). Adherence will be assessed based on the weekly conference calls and data submitted to the DCC on a weekly basis. If it is determined by the study PI that either study protocol is not being followed or that reporting is inadequate at any site, further action will be taken to address these issues. These actions may include additional in-person site visits if appropriate or additional educational/problem-solving sessions by phone regarding the study protocol. Compliance rates and any concerns regarding deviation from study protocol will be reported to the DSMB on a quarterly basis for review and determination if additional measures need to be employed such as protocol changes or discontinuing enrollment at that site.

[figure not shown]
The SLEEP-HD study aims to enroll up to 126 patients with the following distribution among the sites: 76 patients at Seattle and 50 patients at Albuquerque. Tables 1 and 2 and Figure 1 are performance monitoring examples that will be included in future Open DSMB Reports.

Table 1. Cumulative and Current Report Period Study Recruitment

Site	Current Report Period			Cumulative		
	Seattle	Albuquerque	Total	Seattle	Albuquerque	Total
Screened						
Eligible						
Enrolled						
Randomized to CBT-I, trazodone, or placebo						

Table 2. Follow-up rates by site, n / N (%).

	Seattle	Albuquerque	Total
Randomized to CBT-I, trazodone, or placebo			
CATI assessment completed at 7 weeks			

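### Visit Six lets the site investigator start planning continued trazodone before the week-7 primary ISI is taken; a small wording change would put the steps in order

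*Combined protocol and SAP*

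**What the plan says.** Visit Six is set, where feasible, for the first dialysis day of the seventh week. Its list covers bottle collection, pill count, diaries, actiwatch return and the sedative form. For the primary outcome it says only "The patients will be scheduled to receive a phone-call for the 7-week CATI". The last item is "If the patient wants to continue trazodone past the six-week treatment period, the site investigator will facilitate the treatment plan", working with the primary nephrologist or primary care physician.

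The item is not confined to one tablet arm. Section 7.6.3 states: "For patients randomized to trazodone and medication placebo, the visits and related procedures will be identical". Section 5.3.2 has the pharmacy obtain trazodone "from the same manufacturing stock for both clinical sites and prepare matching placebo".

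The week-7 ISI is the primary outcome for Aim One (2.1.1). It is taken in a separate telephone interview (7.6.4.2). Section 6.1 gives the first-choice day as "The day following the first dialysis treatment of the week", then the day after the second session, then the first hour of a dialysis session.

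Section 3.1 bars CBT-I and trazodone as outside treatments for placebo patients during the six treatment weeks and opens both to everyone afterwards. It does not tie that opening to completion of the week-7 ISI.

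**The concern.** A placebo patient who asks to go on with the tablet has no trazodone to continue. Acting on the request means either telling the patient what the tablet was or starting active drug. A trazodone patient may likewise learn the assignment. If this happens before the call, the primary ISI is answered by someone whose knowledge or treatment has just changed.

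The Study Summary and 8.5 call the trial open-label. The matching placebo and identical visits nevertheless imply that trazodone versus placebo is meant to be masked, and it is the only contrast that can be. The ISI is self-reported, so blinded interviewers do not protect against a patient who knows. The sedative form completed at Visit Six looks back seven nights and would miss trazodone started between the visit and the call.

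**Working it through.** **1. Order of events.** Take Visit Six on the first dialysis day of the week. The interview slots in 6.1 then fall as follows:

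- Day after the first session: 1 day later.
- Day after the second session: 3 days later.
- First hour of a session: possibly the same day, so 0 days.

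The usual gap is therefore 0 to 3 days. All these timings are preferences, so it can be longer.

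**2. Is there a rule linking the two steps?** Visit Six states none. Section 7.6.4.2 says "A system-configured email will be sent to the site study coordinator upon successful completion of CATI", but the continuation item is not tied to that email. The heading of 7.6 runs through seven weeks from randomization, and 7.6.4 lists the 7-week call among the treatment-phase interviews. That suggests the call comes first without requiring it.

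**3. Reproducing the plan's power.** Inputs from 8.2.1: SD 6.0, baseline correlation 0.50, target difference 4.0, 110 evaluated patients. Allocation is 1:1:1. Alpha of 0.05 is assumed because the documents give none.

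- Residual SD = 6 × √(1 − 0.5²) = 5.196.
- Patients per arm = 110/3 = 36.7.
- SE of a pairwise contrast = 5.196 × √(2/36.7) = 1.21.
- Noncentrality for means (0, −4, −4) = 36.7 × (2/3) × 4² / 5.196² = 14.5.
- Joint F test on 2 and 105 df: power 0.929, consistent with the stated figure of over 90%.

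**4. Illustrative bias.** The documents give no request rate, disclosure rate or ISI response. Assume a fraction f of placebo patients is affected before the call, from 0 to 0.20 (0 to about 8 of 42), by d = 1 to 2 points each. The placebo mean shifts by s = f × d, from 0 to 0.4 points.

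| s (points) | Joint type I error if placebo patients score worse | Joint power if placebo patients score better |
|---|---|---|
| 0 | 0.0500 | 0.929 |
| 0.1 | 0.0507 | 0.916 |
| 0.2 | 0.0526 | 0.901 |
| 0.4 | 0.0607 | 0.866 |

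The type I column uses noncentrality 36.7 × (2/3) × s² / 5.196². The power column uses 36.7 × (2/3) × (4 − s)² / 5.196². At f = 0.05 (about 2 of 42), s is 0.05 to 0.1 and type I error is 0.0502 to 0.0507. The largest shift, 0.4, is 10% of the 4.0 target and 0.4/1.21 = 0.33 of a standard error.

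**5. Patients whose call is never completed.** There are 84 tablet patients (2/3 of 126). At the planned loss, 84 × 16/126 = 10.7. Appendix Seven, 4.1 expects that "the response rate for the ISI by CATI will be no less than 85% at the 7-week time-point"; at that floor, 84 × 0.15 = 12.6. With equal loss across arms, about 11 to 13 patients would need a fallback rule.

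**The case against.** A reader might infer that the protocol unblinds patients, or gives placebo patients open-label trazodone, before the primary outcome. The documents do not say so. Visit Six describes planning with outside clinicians, not a code-break or dispensing. Open-label drug could be prescribed without disclosure, and a wish could be noted now and acted on later. For drug to affect the ISI, a plan, a prescription and a dose would all have to fit into a few days.

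There is also a partial control. The DSMB charter (1.3.3) requires DSMB approval before potentially unblinding information is given to people directly associated with the study. As worded, that limits giving an assignment to a site investigator. It does not cover open-label prescribing or disclosure to patients. The treatment-phase headings point towards the call coming first, and the Manual of Operations or the consent pages, neither available here, may settle the order.

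The proposed change is itself only partial, because the patient's own physicians can still prescribe before the call. Deferring the plan could also leave a short medication gap.

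Most of this stands and makes the point minor. It does not remove it: the protocol lists a step that can touch the masked contrast and does not say that it follows the primary ISI.

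**Conclusion.** This is a minor, inexpensive improvement, not a flaw that threatens Aim One. The missing sequencing is clear from the text. Its consequence is not: frequency, direction and size are all unknown, and the effect may be zero. The figures above rest wholly on assumed fractions and responses, and only the extreme corner (20% affected by 2 points each) reaches 6.1% type I error or power of 0.87. The case for the change is that it costs little and protects the only masked comparison.

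A reader might extend the point to week 25. The documents do not support that. Section 3.1 deliberately opens all treatments after week 6, and later use is asked about at weeks 13 and 25.

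**What to change.** Reword the last item of Visit Six along these lines: *record whether the patient wishes to continue; the site investigator acts on this, and any assignment is disclosed other than for safety, only once the 7-week interview is complete.*

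- **Trigger.** Use the existing completion email to the coordinator. Count the paper route in 6.1 as completion too, where "the Principal Investigator may authorize the site study coordinator to complete the PROs using paper forms at the bedside".
- **Fallback.** If the interview is never completed, act when a stated week-7 window closes. Section 7.6.4.2 gives no window, so one must be set, for example 7 days after Visit Six.
- **Unchanged.** The patient's own physicians remain free to treat, as 3.1 intends.

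If such a rule already exists in the Manual of Operations, a cross-reference is enough.

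The cost is wording, plus a delay in planning of usually up to 3 days. For the estimated 11 to 13 tablet patients with no completed call, the delay could last until the window closes. A short medication gap is possible, because the bottle is collected at Visit Six as the three-week supply from week 4 runs out.
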